5.2. REPORTING PROCEDURES

This is an ex vivo study. Any AEs that occur as a result of the RP procedure will be reported in line with usual clinical practice. It is not a requirement for the CI to be informed.

6. ASSESSMENT AND FOLLOW-UP

No follow-up or follow-up visits are required for this ex vivo study.

7. STATISTICS AND DATA ANALYSIS

7.1. Sample size calculation

The sample size for diagnostic studies incorporating the prevalence of the PSM was calculated based on expected sensitivity of 0.86 and specificity of 0.96 reported by Baas et al⁷. The authors included 49 patients and analysed 96 prostate sides (a per patient analysis was not carried out). The prevalence of a PSM as detected by standard pathology analysis was 15%. The study did not have an a priori sample size estimation and was not blinded.

The sample size for the planned study was calculated to power a sensitivity analysis in line with the practical application of the new test i.e. that detection of a PSM by FCM would be a safe trigger for a change of intra-operative management.

The following assumptions were made:

- Sensitivity 0.85
- Specificity 0.95
- Prevalence of PSM: 30%. The assumption is based upon a review of 768 historical RPs performed at our centre. The over-all PSM rate was 41% due to high admixture of high-risk patients from the local unscreened population, 47% for high-risk cancers, 37% for intermediate risk cancers and 34% for low-risk cancers.
- Precision: +/- 14 points (a variability deemed sufficient for a pilot study)
- Confidence level: 95%
- Expected dropout rate for poor scans: 10%

Estimated sample size for sensitivity is n=27 PSM patients, inflated by 10% to n=30 for expected drop out. Adjusting for the prevalence of 30% a final sample size of 100 patients is deemed sufficient.

Short Title:	Sponsor:	Version:	Date:
IP8-FLUORESCE	ICHNT	1.2	02 April 2024

Since the true prevalence of PSMs for the study cohort is not known, an interim assessment of observed PSM rate is planned a priori. This will be used to adjust the sample size accordingly.

Assessment of the interim PSM rate is planned after 50 patients by a pre-specified independent assessor nominated before the start of the study. The assessment is based on the clinical histopathology reports for each patient which includes PSM status.

Example for sample size adjustment after interim analysis of prevalence are presented as follows: If the observed PSM rate is 25% the sample size would need to be increased to 120 patients. Conversely, if the observed PSM rate is 35% the sample size would decrease to 86 patients.

Full details of planned statistical summaries and analyses will be outlined in a pre-defined, signed and dated statistical analysis plan before any analyses are performed. Any deviations from the analysis plan will be fully documented with reasons for doing so.

Data and all appropriate documentation will be stored for 10 years after the completion of the study.

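### Section 7.1 needs a fixed count of PSM patients, but resets total N once from the rate in 50 patients and lets N fall below 100

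*Protocol*

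**What the plan says.** Section 7.1 of the Protocol assumes a sensitivity of 0.85, a precision of plus or minus 14 points at 95% confidence, a PSM prevalence of 30% and 10% loss to poor scans. From these it derives 27 PSM patients, 30 after inflation and 100 patients in total. The prevalence is set below the centre's record of 768 operations: "The over-all PSM rate was 41% due to high admixture of high-risk patients from the local unscreened population". The lowest subgroup rate quoted there is 34%, for low-risk cancers.

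Because the study's own rate is unknown, there is one interim look: "Assessment of the interim PSM rate is planned after 50 patients by a pre-specified independent assessor nominated before the start of the study". It uses the clinical histopathology reports. Two examples show its effect: "If the observed PSM rate is 25% the sample size would need to be increased to 120 patients", and, in the other direction, "if the observed PSM rate is 35% the sample size would decrease to 86 patients".

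Section 7.1 states no floor at 100, no upper limit and no requirement that 30 PSM patients be reached. The study summary (Duration) and section 4.4 tie the end of recruitment to the required or target number, but neither makes a count of PSM patients the stopping condition.

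**The concern.** The precision of a sensitivity estimate depends on how many reference-positive patients there are, not on total N. The plan sets a target for that count but controls it indirectly, through a rate estimated once in 50 patients. At a true rate of 30% such a rate has a 95% half-width of about 13 points. A rate that is high by chance cuts N, and the remaining patients then tend to yield too few PSMs. A rate that is low by chance inflates N without limit: 10 of 50 gives 150. The same reports that supply the rate would supply the count directly. At stake is whether the study ends with the number of PSM patients its sample size section asks for.

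**Working it through.** **Inputs (all Protocol section 7.1).** Sensitivity 0.85; half-width 0.14; 95% confidence; 10% poor scans; target 27 PSM patients, 30 inflated; planning prevalence 30%; historical rate 41% overall and 34% to 47% by risk group; interim look at 50 patients.

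**The plan's own figures.**
- Wald requirement: 1.96² × 0.85 × 0.15 / 0.14² = 24.99, so 25. The stated 27 is slightly more generous.
- 27 / 0.9 = 30, and 30 / 0.30 = 100.
- Interim examples: 30 / 0.25 = 120 and 30 / 0.35 = 85.7, so 86. Both fit N = 30 / observed rate.

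**Precision of the interim rate.** 1.96 × √(0.3 × 0.7 / 50) = 0.127. For 15 of 50 the Wilson interval is 19% to 44%.

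**Chance of a shortfall.** Let X ~ Binomial(50, p) be the PSM count at the look, N(X) = max(50, 30 / (X/50) rounded up), and the final count X + Binomial(N(X) − 50, p). Exact enumeration gives:

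| True PSM rate p | 30% | 35% | 41% |
|---|---|---|---|
| P(N cut below 100) | 43% | 72% | 93% |
| Mean N under the rule | 105.7 | 89.7 | 75.9 |
| P(<30 PSM), plan's rule | 41.0% | 38.9% | 34.9% |
| P(<30), N = 30/p with p known | 46% | 45% | 42% |
| P(<30), fixed N = 100 | 46.2% | 12.4% | 0.9% |
| P(<30), look may only raise N | 19.8% | 5.3% | 0.4% |
| Mean N, look may only raise N | 112 | 104 | 101 |
| P(<27 enrolled), plan's rule | 14.1% | 8.9% | 3.9% |

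**The plan's downward example.** If 17 or 18 of 50 are positive (34% or 36%), N is cut to 86 and the true rate is 30%, the chance of ending below 30 is 74% or 61%.

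**Effect on precision.** The Wald half-width is 12.8 points with 30 evaluable PSM patients, 13.5 with 27 and 14.0 with 25. If each scan is lost at random with probability 10%, the chance of fewer than 25 evaluable PSM patients under the plan's rule is 21.8% at a true rate of 30% and 13.5% at 41%. With exactly 30 PSM patients enrolled it is P(Binomial(30, 0.9) < 25) = 7.3%.

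**Recruiting to a count of 30.** Without a cap, mean N is 30/p: 100 at 30%, 86 at 35% and 73 at 41%. At 30% the standard deviation of N is √(30 × 0.7) / 0.3 = 15, against 26 under the plan's rule. With a cap, the shortfall at 30% is P(Binomial(cap, 0.3) < 30): 24% for 110, 10% for 120 and 0.2% for 150.

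**The case against.** The strongest reply is that a shortfall in about two of five runs is not mainly the interim rule's doing. Any N chosen so that the expected count is 30 falls below 30 nearly half the time. With the true rate known exactly the figure is 42% to 46%, so the plan's rule does a little better than perfectly informed sizing. At 30% it also beats a fixed N of 100. This stands. A reader might infer that the noise of a 50-patient rate creates the whole 35% to 41%; the calculation does not support that.

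Second, 30 is not the precision threshold. It already contains the dropout allowance, and counts of 27 to 29 are small misses. This also stands. A reader might infer that sensitivity precision fails in two of five runs; it does not.

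Third, comparing mean N alone is not like for like. At 30% the rule's 105.7 patients yield 105.7 × 0.3 = 31.7 PSMs on average, so its extra patients buy extra PSMs. Likewise, N=100 at 41% buys about 41 PSMs, more than the stated precision needs. It would therefore be wrong to say that the rule wastes patients.

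Fourth, one blinded re-estimation of a prevalence by an independent assessor is a recognised design, and a floor or cap could be set in the statistical analysis plan. The intention is sound. However, section 7.1 itself gives a reduction to 86 as an example, so the downward step is fixed in the protocol.

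**Conclusion.** The point holds as a moderate design weakness. The target is a count; the rule controls it through one noisy rate and permits a reduction. The clearest harm is that reduction. At true rates of 35% and 41% it raises the chance of fewer than 30 PSM patients from 12% and 1% (fixed N=100) to 39% and 35%. The historical rates in section 7.1 are all 34% or higher, so a cut is the likely outcome if the study cohort resembles them. At 30% the rule is slightly better than no adaptation.

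The figures assume that N = 30 / observed rate applies at every observed rate, with no floor other than the 50 already enrolled and no cap; that patients are independent with a constant PSM rate; and, for evaluable counts, that scans are lost at random. The protocol gives only two examples, so the first assumption is an extrapolation, though both examples fit it exactly.

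**What to change.** **Preferred.** In section 7.1, replace the one-off rescaling with this rule: recruit until the independent assessor has counted 30 patients with a PSM on the clinical histopathology reports, up to a stated maximum N. Keep the 50-patient look for forecasting only. Align the recruitment target in section 3.1 and the Duration entry in the study summary. Count PSM status as section 7.1 uses it. Section 3.2 restricts the primary outcome to Gleason 7 or above at the margin, but section 7.1 says only that the clinical reports give PSM status, while section 3.1 places grade at the margin in the re-report made after recruitment. The narrower definition therefore cannot be assumed to be countable during recruitment.

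The shortfall is zero only without a cap, so the cap should be chosen knowingly: at 30% prevalence, 120 leaves about 10% below 30 and 150 about 0.2%. Mean N is at most about 100 at 30% and 73 at 41%.

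**Cost.** The assessor and the reports are already in the plan. Final N is not known in advance, reporting lag may add a few patients, and the observed PSM rate is biased upwards by about p(1 − p)/30 = 0.3 × 0.7 / 30 = 0.7 points. Sensitivity should be unaffected, because the FCM images are not read until recruitment has ended.

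**Minimal alternative.** Let the interim look only raise N above 100, with a stated cap. Before any cap this gives the shortfall risks and mean N shown in the table. It is less efficient at high prevalence but keeps the present structure.

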8. REGULATORY ISSUES

8.1. ETHICS APPROVAL

This study was granted ethical approval via the Imperial College Healthcare Tissue Bank (ICHTB) which is approved by Wales REC3 to release human material for research. The Human Tissue Authority (HTA) licence reference is 12275. Research ethics committee (REC) approval is granted under reference 22/WA/0214. ICHTB is supported by the National Institute for Health Research (NIHR) Biomedical Research Centre (BRC) based at Imperial College Healthcare NHS Trust and Imperial College London. Further information on Imperial's BRC can be found here:

https://imperialbrc.nihr.ac.uk/about-us/acknowledgement/.

Ethics for tissue collection from University College London Hospital was granted on 12th March 2024 by the UCL/UCLH Biobank for Studying Health and Disease (Project reference NC36.24).

Ethics for tissue collection from Guy's and St Thomas' NHS Foundation Trust was granted on 26th February 2024 by the King's Health Partners Cancer Biobank (HTA Licence No: 12121, REC No: 23-EE-0005).

Short Title:	Sponsor:	Version:	Date:
IP8-FLUORESCE	ICHNT	1.2	02 April 2024

The study will be conducted in accordance with the recommendations for physicians involved in research on human subjects adopted by the 18th World Medical Assembly, Helsinki 1964 and later revisions.

8.2. TRIAL REGISTRATION

The study will be registered on on the ISRCTN trial registry in accordance with requirements of the International Committee of Medical Journal Editors (ICMJE) regulations.

8.3. CONSENT

Consent for use of human tissue for medical research is part of the standard consent process for patients undergoing surgery or biopsy at Imperial College Healthcare NHS Trust. Patients receive an information leaflet via the ICHTB prior to signing consent. Only those patients who have signed this subsection of the surgical consent form will be included.

8.4. CONFIDENTIALITY

The investigator must ensure that the subject's confidentiality is maintained. On the CRF or other documents submitted to the Sponsors, subjects will be identified by a subject ID number only. Documents that are not submitted to the Sponsor (e.g. signed informed consent form) should be kept in a strictly confidential file by the investigator.

The investigator shall permit direct access to subjects' records and source document for the purposes of monitoring, auditing, or inspection by the Sponsor, authorised representatives of the Sponsor, NHS, Regulatory Authorities and REC.

The Chief Investigator will preserve the confidentiality of participants taking part in the study and is registered under the Data Protection Act.

8.5. INDEMNITY

Imperial College Healthcare NHS Trust holds standard NHS Hospital Indemnity and insurance cover with NHS Resolution for NHS Trusts in England, which apply to this study.

8.6. SPONSOR

Imperial College Healthcare NHS Trust will act as the main Sponsor for this study.

Short Title:	Sponsor:	Version:	Date:
IP8-FLUORESCE	ICHNT	1.2	02 April 2024

8.7. FUNDING

A grant of £60,000.00 for this study was generously awarded by The Urology Foundation (TUF) through the Innovation and Research Award 2023, funded by the John Black Charitable Foundation.

Short Title:	Sponsor:	Version:	Date:
IP8-FLUORESCE	ICHNT	1.2	02 April 2024

9. STUDY MANAGEMENT

A trial management group (TMG) including the Chief Investigator, co-investigators and key collaborators, trial statistician and trial manager. The TMG will be responsible for day-to-day conduct of the trial and operational issues. Details of membership, responsibilities and frequency of meetings will be defined separately. A lay person will be included.

10. PUBLICATION POLICY

Information concerning the study, patent applications, processes, scientific data or other pertinent information is confidential and remains the property of the Sponsor. The investigator may use this information for the purposes of the study only. It is understood by the investigator that the Sponsor will use information developed in this clinical study and, therefore, may disclose it as required to other clinical investigators. In order to allow the use of the information derived from this clinical study, the investigator understands that he/she has an obligation to provide complete test results and all data developed during this study to the Sponsor. Verbal or written discussion of results prior to study completion and full reporting should only be undertaken with written consent from the Sponsor. Therefore, all information obtained as a result of the study will be regarded as CONFIDENTIAL, at least until appropriate analysis and review by the investigator(s) are completed. A Clinical Study Report summarising the study results will be prepared and submitted to the ICHTB within a year of the end of study.

